We recently completed the first RCT of **Dutasteride for the reduction of heavy** drinking in men. Results support further examination of dutasteride as a treatment option for AUD. In total 189 treatment seeking men were enrolled of which 24 were screen failures and 23 failed to return for the baseline visit leaving 142 subjects randomized to medication (dutasteride n=74). Seven subjects did not return after the baseline randomization visit providing a modified intention to treat sample of 135 subjects (68 dutasteride and 67 placebo) who provided drinking data post-randomization. One hundred seven subjects completed the entire 12-week treatment. The mean number of treatment weeks completed were not different between arms (dut 10.2 vs. pbo 10.7). 3α androstanediol glucuronide levels were decreased by 80% in the dutasteride group at both 6 and 12 weeks vs. 0% in pbo treated subjects confirming the anticipated pharmacological effect for our study design. There were no significant differences between groups (dutasteride vs. pbo) for measures of alcohol consumption during the 60-days prior to screening including the number of standard drinks (SD) per week (48.8 vs. 47.3), number of heavy drinking days (HDD, 5 or more drinks for men) per week (5.2 vs. 5.2), or abstinent days per week (0.67 vs. 0.62). While the dutasteride group were more likely to have had a prior episode of treatment for alcohol use (59% vs. 40%, p=0.03) the number of DSM-IV AD criteria did not significantly differ between groups (4.3 vs. 4.0).

[figure not shown]
Safety. There were no study related serious adverse effects. The proportion of subjects exposed to study medication who reported at least one non-serious adverse

[figure not shown]
effect was not significantly different for the dutasteride vs. pbo groups 71.6% vs. 67.1% similarly, the number of side effects per subject was not different between dutasteride and placebo groups, 1.36 ± 1.46 vs. 1.03 ± 1.10 . Adverse events that were reported by more patients in the dutasteride compared with the placebo arm included stomach discomfort (16.4% vs. 4.5%, p=0.04) and reduced libido (9.0% vs. 0%; p=0.03). More subjects in the dutasteride arm (n=4) than the pbo arm (n=1) stopped medication due to side effects. Beck Depression Inventory scores were low in both treatment arms at baseline (10.4 dut vs. 7.5 pbo) and reduced to a similar degree during the 12-week treatment (-3.3 dut vs. -2.4 pbo, t=0.6; p=0.5).

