Drinking outcomes. Comparison of treatment groups for the modified intention to treat sample (N=135) on the primary outcomes of HDD/week and drinks/ week using generalized linear mixed models (GLMM) showed significant treatment x time interactions (HDD F=9.2; df=1,1406, p=0.002 and SD/wk F=4.8, df=1,1406, p= 0.028). While a minority of our subjects smoke, in view of prior reports of differential medication effects among smokers vs. non-smokers for naltrexone we examined GLMM models that included smoking status, treatment condition, treatment x time, and treatment x smoking as predictors, and identified significant 2-way interactions of treatment x time (F=9.1, df=1,1404, p=0.003 and F=4.4, df=1,1403, p=0.035 for HDD and SD/wk, respectively), and treatment x smoking (F=8.4, df=1,1404, p=0.004 and F=10.9, df=1,1403, p=0.001 for HDD and SD/wk, respectively), such that smokers (n=12) treated with dutasteride drank more throughout the treatment period than smokers treated with pbo (n=12), while the opposite response was observed for non-smokers (dutasteride=56; pbo=55). Smokers and nonsmokers did not differ on baseline drinking, age, Spielberger State Anxiety (SAI) or Beck Depression Inventory (BDI) scores. The interaction of drug x smoking status may relate to the induction by tobacco of phase I metabolism cytochrome P450 and aldo-keto reductase enzymes (Nagaraj, Beckers et al. 2006), the latter of which are involved in neuroactive steroid biosynthesis and metabolism. A prior study showed a positive correlation between serum cotinine levels and the neuroactive steroid allopregnanolone in a sample of 28 men (Marx, Trost et al. 2006). Somewhat surprisingly, with limited exceptions (Fucito, Park et al. 2012, Litten, Ryan et al. 2013, Schacht, Randall et al. 2017) reports for recent RCTs for AUD either did not report the proportion of smokers (Johnson, Ait-Daoud et al. 2003, Johnson, Rosenthal et al. 2007, Johnson, Ait-Daoud et al. 2011, Johnson, Seneviratne et al. 2013, Kranzler, [name] et al. 2014) or did not include smoking status in the analysis of outcomes (Anton, O'Malley et al. 2006, Anton, Myrick et al. 2011, Fertig, Ryan et al. 2012, Litten, Fertig et al. 2012). Interestingly, in the reports by Fucito et al. (Fucito, Park et al. 2012) and Schacht et al. (Schacht, Randall et al. 2017) naltrexone only benefited drinkers who also smoked while our results with dutasteride indicated only non-smokers were responsive, presumably reflecting distinct mechanisms of change. We will include smokers in the proposed study to further evaluate our initial findings. Dutasteride nonresponsive smokers in phase 1 may experience treatment responsive to naltrexone in phase 2 of the proposed study which would support use of smoking as a factor in individualized treatment recommendations.

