
For the majority non-smoker group (n=111) there was a significant interaction of medication group by treatment week (HDD/wk F=6.2, df=1,1183, p=0.013; and SD/wk F=4.7, df=1,1183, p=0.031) **Figure 1**, such that dutasteride treated subjects reduced drinking over time more than placebo subjects. During the last 4 weeks of the 12-week treatment period, the proportion of subjects with a \geq 60% reduction in SD/wk compared with screening (which represents a clinically meaningful reduction from a group average of 48 SDs/wk to less than 20) was significantly greater for the dutasteride vs. the pbo group [49% vs. 20%; χ^2 =8.3, p=0.004; OR=3.8 (95% Cl=1.5-9.8)]. Additionally, among the 91 per protocol completers, during the last month of treatment 33% of subjects in the dutasteride arm had no heavy drinking and 27% no hazardous drinking (no HDDs and no more than 14 SD/wk) compared with 11% and 2% of pbo- treated subjects respectively [no HDD days [χ^2 =6.7, p=0.01; OR = 4.1, NNT=5]; and no hazardous drinking [χ^2 =11.1, p=0.001; OR = 16.4, NNT=4]. The additional analysis described below focuses on the group of 111 non-smokers.

[figure not shown]
Figure 1. Heavy Drinking Days per week (left) and Standard Drinks per week (right) for pbo vs dutasteride treated nonsmokers (mean±SEM).

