2.C.9.b. Sample size considerations: For Aim 1, the proposed sample size of 160 completing the phase 1 12-week treatment (80 per arm), has 80% power to show statistical significance (α =0.05) for medium-size effects, d=0.4, such as observed in our initial RCT of dutasteride in men (d=0.38 for change in SDs/wk from baseline to last month of treatment comparing dutasteride and pbo n=91]. For Aim 2a, assuming 80% power and α =0.05 and a sample of 40 responder subjects continuing on dutasteride, the non-inferior margin limit would be an increase of 0.67 HDD/wk or 5 SDs/wk during the second 12 weeks dutasteride treatment. For Aim 2b, a sample of 64 placebo non-responders crossing over to dutasteride for phase 2 would have 90% power to detect a medium effect size for reduction in drinking in phase 2 using a within-subjects t-test. For Aim 3, using the GLMPOWER procedure and the between cell effects for the preliminary data presented above (section 2.B.2) for the 2-way interaction of drinking to cope x drug, a sample of 160 subjects in phase 1 would have 80% power to detect the magnitude of this interaction seen in the preliminary dataset.

Table 3. Timeline for recruitment and other study objectives:

Dutasteride AUD#2 protocok V9 (05-18-2022)

IRB NUMBER: 19-147-2 IRB APPROVAL DATE: 02/27/2024

Staff training & study prep										
Patient enrollment & randomizing 5/mo										
3- and 6-month follow-up										
Data entry & cleaning										
Data analysis & Report writing										

Section 3. PROTECTION OF HUMAN SUBJECTS

3.A Risks to Human Subjects

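### Aim 1's stated 80% power does not follow from its own inputs under a two-sided test: they give 71% at d=0.4 and 67% at the observed d=0.38, before baseline adjustment

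*Combined protocol and SAP*

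**What the plan says.** Section 2.C.9.b (Sample size considerations) bases Aim 1 on 160 subjects completing the 12 weeks of phase 1, 80 per arm. It says this sample "has 80% power to show statistical significance (α =0.05) for medium-size effects, d=0.4". The effect size is tied to the first trial in men, reported there as "d=0.38 for change in SDs/wk from baseline to last month of treatment comparing dutasteride and pbo n=91".

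The Aim 1 sentence gives no test, no sidedness and no adjustment. The same paragraph does name a method for Aim 2b (a within-subjects t-test) and for Aim 3 (the GLMPOWER procedure). The Aim 3 statement, "a sample of 160 subjects in phase 1 would have 80% power to detect the magnitude of this interaction", concerns the drinking-to-cope by drug interaction. The Aim 1 sentence is therefore the only power statement for the main phase 1 treatment effect.

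Section 2.C.9.a.2 (Efficacy) plans generalized linear mixed models with baseline drinking as a covariate. Neither section says whether testing is one-sided or two-sided. Section 2.B.2 reports the earlier trial's treatment-by-time tests as "HDD F=9.2; df=1,1406, p=0.002 and SD/wk F=4.8, df=1,1406, p= 0.028" in the modified intention-to-treat sample and "HDD/wk F=6.2, df=1,1183, p=0.013; and SD/wk F=4.7, df=1,1183, p=0.031" in the non-smokers.

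**The concern.** When a power statement gives a sample size, a standardised difference and alpha and nothing else, the usual reading is a two-sided two-sample comparison. Read that way, the four numbers in the Aim 1 sentence do not fit together, because 80 per arm at d=0.4 falls well short of 80%.

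What is at stake is how a null phase 1 result would be read. Under this reading the chance of missing a true d=0.4 is 29% rather than 20%, and at the observed 0.38 it is 33%. A reader who takes the 80% at face value would give a negative result more weight than the stated inputs support. If the 80% does come from a one-sided test, that is a material design choice that should be visible in the plan.

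**Working it through.** **Inputs.** From 2.C.9.b: n = 80 completers per arm, d = 0.4, observed d = 0.38 for change in drinks per week, alpha = 0.05, stated power 80%. From 2.C.3.d: 1:1 allocation. From 2.C.2: 190 to be randomised, so 95 per arm. Drop-out is already taken out of the 80 per arm.

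**Formula.** Two-sample t-test with df = 2n − 2 and noncentrality d × √(n/2). Power is the probability that the noncentral t statistic passes the critical value.

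**Step 1: reproduce the plan's 80%.** A one-sided 0.05 test comes close. Noncentrality = 0.4 × √40 = 2.530, critical value 1.655 on 158 df, power 80.9%. At d = 0.38 the noncentrality is 2.403 and one-sided power is 77.3%.

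**Step 2: two-sided on the same inputs.** The critical value is 1.975.

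| n per arm | d = 0.4 | d = 0.38 |
|---|---|---|
| 80 (completers, as stated) | 71.0% | 66.6% |
| 95 (all randomised) | 78.3% | 74.1% |

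The smallest d with 80% two-sided power at 80 per arm is 0.446. Reaching 80% two-sided would take 100 per arm at d = 0.4, or 110 per arm at d = 0.38.

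**Step 3: which sidedness do the documents point to?** The earlier trial's tests in 2.B.2 are F tests on 1 numerator df, so each reported p-value can be checked.

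| F (df) | Reported p | Two-sided p | Half of it |
|---|---|---|---|
| 9.2 (1, 1406) | 0.002 | 0.0025 | 0.0012 |
| 4.8 (1, 1406) | 0.028 | 0.0286 | 0.0143 |
| 6.2 (1, 1183) | 0.013 | 0.0129 | 0.0065 |
| 4.7 (1, 1183) | 0.031 | 0.0304 | 0.0152 |

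The reported values are two-sided to within rounding. They come from mixed-model terms, so they bear on sidedness only and do not show that an unadjusted test was meant.

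**Step 4: what could baseline adjustment recover?** Let r be the baseline-to-outcome correlation. The documents do not give it, so r is an assumption here. In a linear model with equal variances, the change score has variance proportional to 2(1 − r) and the adjusted outcome to 1 − r². A d expressed on the change-score SD therefore becomes d × √(2/(1 + r)) after adjustment. Setting this to at least 0.446 gives:

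- d = 0.4: r ≤ 2 × (0.4/0.4457)² − 1 = 0.61
- d = 0.38: r ≤ 2 × (0.38/0.4457)² − 1 = 0.45

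Adjusted two-sided power at 80 per arm over a range of r:

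| Assumed r | d = 0.4 | d = 0.38 |
|---|---|---|
| 0.4 | 85% | 81% |
| 0.5 | 83% | 79% |
| 0.6 | 80% | 76% |
| 0.8 | 76% | 71% |

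This is a linear approximation to the planned binomial and negative binomial mixed models, not a power calculation for them.

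**The case against.** The strongest reply is that 71% is the power of an analysis the plan does not contain. Phase 1 drinking outcomes are to be analysed by a mixed model that controls for baseline drinking. On the change-score scale, adjustment cannot lower power in the linear approximation, so 71% is a floor approached only as r nears 1. For moderate correlations the adjusted power at d=0.4 is 80% or more. This stands, and it is why the 71% and 67% must be labelled as figures before adjustment. It does not rescue the sentence as written, because 2.C.9.b neither refers to the adjusted model nor gives a correlation. At the observed d=0.38 the condition on r is also tighter.

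A second reply is that the figure can be reproduced one-sided, so nothing has been miscalculated. The reproduction is correct, but no one-sided test is declared, the earlier trial's tests were two-sided, and d=0.38 gives only 77% one-sided. A third is that 0.4 is a rounded 0.446. That value would be 17% above the 0.38 offered as its basis (0.446/0.38 = 1.17).

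A reader might go further and infer that the 80% is a proven arithmetic slip, or that phase 1 is underpowered. The documents do not support either, since an undeclared one-sided or adjusted calculation could lie behind it. Nor do they support the inference that the basis of the figure is unknowable. The analysis set is stated as the 160 completers. The scale of d is indicated by the description of 0.38 as a change from baseline. The source of the 91 is largely recoverable: 2.C.9.b names the first trial in men, and 2.B.2 refers to "among the 91 per protocol completers" in the paragraph on the non-smokers.

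**Conclusion.** The point holds as a mismatch between the stated power and the stated inputs. With 80 completers per arm and two-sided alpha 0.05, a comparison of change in drinks per week has 71% power at d=0.4 and 67% at d=0.38, which is 9 and 13 percentage points below the stated 80%. Counting all 95 per arm narrows the gap but does not close it.

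These figures assume a two-sample t-test, equal arms and no baseline adjustment. The two-sided reading rests on convention and on the earlier trial's reported p-values. Whether the planned adjusted model reaches 80% depends on a correlation the documents do not give: at most about 0.61 at d=0.4 or 0.45 at d=0.38, on the change-score SD and in a linear approximation. The 80% is thus attainable under the planned analysis but is not shown. It should be corrected because it is the only power figure for the main phase 1 treatment effect.

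**What to change.** In 2.C.9.b, replace the Aim 1 power sentence with wording such as:

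*160 completers (80 per arm) give 71% power at d=0.4 and 67% at d=0.38 (two-sided alpha 0.05, before baseline adjustment); 80% is reached at d=0.45.*

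If the sponsor wishes to keep 80%, replace the present claim with a two-sided, baseline-adjusted calculation that matches the model in 2.C.9.a.2, with the assumed baseline-to-outcome correlation shown and labelled as an assumption.

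The cost is a less favourable stated power unless the adjusted calculation is documented. No extra patients are needed and the planned analysis does not change.

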Aim 2. Aim 2A: To examine whether the reduction in drinking in treatment responders (defined as ≥60% reduction during weeks 9-12) is maintained in a 12-week, phase 2 extension of the initial treatment condition (pbo or dutasteride). This will help to determine the clinical utility of dutasteride as a treatment for AUD, which is a chronic, relapsing disorder. Aim 2B: Increase the number of dutasteride double-blind treated subjects by including in the 12-week phase 2 a cross-over for pbo non-responders to dutasteride and for dutasteride non-responders to naltrexone, a medication with a different mechanism of action compared with dutasteride.

We hypothesize that reductions in drinking for dutasteride responders in phase 1 will be maintained during the 12-week extension period. Additionally, we hypothesize that phase 1 non-responders on pbo will have significant reductions in drinking when crossed over to dutasteride in the second 12-week phase. Further, we expect that a portion of dutasteride non-responders will have significant reductions in drinking when treated with naltrexone, consistent with models of individual genetic and environmental factors producing differences in individual subject responses to medications with different mechanisms of action.

Aim 3. To examine baseline measures of drinking to cope, trait anxiety, perceived life stress, or early life adversity predict dutasteride treatment efficacy, and secondarily, whether a common genetic variation, rs1360780, in the *FKBP5* gene, which encodes a modulator of the intra-cellular steroid hormone signaling system and HPA stress response system, moderates dutasteride treatment response as an interactive effect with these negative affect/life stress measures. We hypothesize that dutasteride treatment benefits

relative to placebo will be greatest for subjects reporting more drinking to cope, greater anxiety, perceived stress or a history of trauma/adversity, particularly for those who are carriers of the *FKBP5* rs1360780 T-allele.

Section 2. RESEARCH STRATEGY

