The proposed study will extend these results by including both sexes and extend our analysis of the relationship of baseline drinking to cope (DTC) and anxiety by adding baseline standardized questionnaires measuring trait anxiety (STAI), early life adversity (ACES), and a perceived stress scale (PSS) which in other settings was more predictive of health care utilization than stressful life event counts (Cohen, Kamarck et al. 1983). Women are expected to have a greater likelihood of elevated DTC, ACES, trait anxiety scores (Smith and Randall 2012) which will enrich our sample in subjects potentially more responsive to dutasteride vs. pbo. We will use separate randomizations for women vs. men and include dichotomized scores for DTC and *FKBP5* risk allele carrier status in our URN randomization to balance for these potential predictors of efficacy. This study may identify easy to score pre-treatment measures such as the CDMQ, ACES, STAI, PSS and genotype that could be clinically useful for making personalized treatment recommendations regarding use of dutasteride to reduce heavy drinking.

2.C. Experimental Approach / Research Plan

2.C.1. General Design: The study will be conducted in the UCHC Clinical Research Center (CRC) clinic. Random assignment to initial treatment group and double-blind conditions will be maintained throughout the study. The study consists of two 12-week phases (**Table 1**), the first being a 12-week parallel-groups comparison of dutasteride and pbo to evaluate the safety and efficacy of dutasteride 1 mg/day in reducing the likelihood of drinking and heavy drinking in a sample of treatment-seeking men and women with AUD. In the second 12-week phase, responders in phase 1 (defined as a ≥60% reduction in SD/wk for weeks 9-12 compared with screening) will continue on their initial medication assignment, while non-responder subjects treated with placebo will cross over to dutasteride, and non-responder subjects treated with dutasteride will cross over to naltrexone. This design maintains double blind conditions in both phases 1 and 2 and is innovative. This design will: i) promote retention and recruitment, as subjects who do not respond to treatment in phase 1 will cross-over to an active FDA approved medication for AUD, ii) provide two comparisons to examine dutasteride efficacy, a between-subjects

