comparison in phase 1 and a within-subjects test in phase 2 for patients treated with pbo in phase 1 and dutasteride in phase 2, iii) allow evaluation of whether reductions in drinking are maintained with ongoing treatment for phase 1 dutasteride responders, and iv) provide preliminary data on whether dutasteride non-responders show reductions in drinking when crossed over to naltrexone, an established medication for AUD with a different mechanism of action compared with dutasteride.

Three and six-month follow-up visits following the completion of the 24-week treatment phase will evaluate the durability of treatment effects, allow measurement of the degree to which dutasteride effects on 5AR inhibition have been reversed following 12- or 24-week exposures and to maintain contact with female participants to remind them of the importance of effective contraception for 6 months following treatment.

Table 1. Expected Patient Distribution for Phase 1 and 2.

Phase 1	Phase 1	Phase 1	Phase 2	Phase 2 Statistical contrasts
Treatment	Statistical	Expected Tx	Treatment	
	contrasts	response groups		
Dutasteride n=95 (grp A)	Between-subject contrasts using GLMM Dut vs. Pbo for DVs HDD/wk and SD/wk;.	Dut-R (wk 9-12 Response n=40) Dut-NR (wk 9- 12 Non-Response n=40)	Dut-R dutasteride Dut-NR naltrexone	Within-subject interrupted time series regression using mixed models. Dut-R: Is dut response maintained? Dut-NR: Do dut NRs respond to naltrexone?
	Moderating			
Pbo n=95 (grp B)	effects of genotype, baseline state vs. trait anxiety, perceived stress and interaction with FKBP5 genotype	Pbo-R (wk 9-12 Response n=16) Pbo-NR (wk 9- 12 Non-Response n=64)	Pbo-R pbo Pbo-NR dutasteride	Pbo-R: insufficient sample for statistical comparison. Pbo-NR: Do pbo NRs respond to Dut?

Phase 1 response ≥ 60% reduction SD/wk for wk 9-12 vs baseline (current study 49% response rate for dut vs. 20% pbo). dutasteride 1 mg/day; naltrexone 50 mg/day.

2.C.2. Patients: Drinkers who want to reduce or stop drinking will be recruited using advertisements in radio and print media, by posting/distributing recruitment materials in community settings, informational mailings to area clinicians and by referral from UConn Health medical and dental clinics in at our main campus in Farmington CT together with

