For the phase 1 comparison of dutasteride and pbo over time, efficacy analyses will be performed using generalized linear mixed (GLMM) models implemented in SPSS. GLMM incorporates within subject correlation effects important in examination of repeated measures, can incorporate multiple covariates, interactions, random and fixed effects, nonnormal distributions, and is often recommended for designs such as proposed (Mallinckrodt C 2017). Medication group will be treated as a factor and treatment week as a continuous covariate. Sex, smoking status, treatment goal (stop vs. reduce drinking), and use of concurrent medication for co-morbid psychiatric conditions will also be examined as baseline between-subject covariates. Medication group, week, and the other covariates will be modeled as fixed effects, and the intercept will be modeled as random effects. For the outcome HDD/wk a binomial distribution with logit link will be used where the number of HDD during the week will be the numerator and number of observed days the denominator. For the outcome SD/wk a negative binomial distribution with log link will be used. An interaction term between medication group and the week term(s) will be used to evaluate whether the efficacy of dutasteride compared to pbo in reducing drinking varies over time. Interaction effects of sex and treatment condition will also be examined. Pretreatment drinking will be controlled using baseline TLFB drinking data as a covariate. The robustness of results will be evaluated by running the model under three different conditions: 1) modified intention to treat using all available outcome information from subjects with at least 1 post-randomization visit, 2) data from 12-week per protocol completers, and 3) multiple imputation using 10 imputed data sets with weekly drinking and baseline covariates thought predictive of the outcomes or missingness included in the imputation phase.

For aim 2, phase 2 outcomes, the within-subjects analysis will compare drinking during phase 1 against phase 2 for three groups: a) patients responsive to dutasteride in phase 1 and continuing on dutasteride for an additional 12-weeks in phase 2, to examine whether the response is maintained with continued treatment; b) phase 1 non-responders crossed over from pbo in phase 1 to dutasteride in phase 2 to provide a second contrast using an A-B design of the efficacy of dutasteride compared with pbo; and c) phase 1

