dutasteride arm non-responders switched to naltrexone to determine whether naltrexone is effective in reducing drinking in dutasteride non-responders. An interrupted time series regression using mixed models will be used (Wagner, Soumerai et al. 2002, mallinckrodt and Lipkovich 2017), where in addition to a variable for week an indicator variable for phase, a second weekly variable that is sequentially coded beginning at phase 2 and the interaction of the two variables will be included in the model. The phase indicator variable will measure change when entering phase 2 and the second weekly variable will measure change in trajectory deviating from phase 1. In addition, a restricted period analysis focusing on the average of the last 4 weeks of phase 1 compared to average of the last 4 weeks of phase 2 will be conducted. This may be more sensitive if the first few weeks of each phase show limited initial response, which would dilute the effects for phase and the interaction for the interrupted regression model. For the first group, dutasteride responders, a non-inferiority test will be used where the non-inferior margin will be 20% above the drinking levels during phase 1. For the latter two groups of non-responders a superiority test will be used.

For aim 3, analysis of drinking outcomes will be repeated including baseline measures of DTC, trait anxiety, perceived stress, adverse child event count and genotype for the *FKBP5* rs1360780 SNP (CC vs. T-carrier) as additional between-subject factors together with the 2- and 3-way interactions of medication condition with DTC, SAI, PSS or ACES measures and *FKBP5* genotype. We will include both Blacks and Caucasians in the pharmacogenetics analysis as our prior study showed similar interactions of *FKBP5* genotype with life stress on drinking measures in both Black and Caucasian college students (Lieberman, Armeli et al. 2016).

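### Aim 2a non-inferiority test: the 20% and 5 drinks/wk margins are not reconciled, and a whole-phase-1 reference would let a relapse pass as a maintained response

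*Combined protocol and SAP*

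**What the plan says.** Aim 2A (Specific Aims) asks whether "the reduction in drinking in treatment responders (defined as ≥60% reduction during weeks 9-12) is maintained" in the 12-week extension. Section 2.C.1 gives the same window: "responders in phase 1 (defined as a ≥60% reduction in SD/wk for weeks 9-12 compared with screening").

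Section 2.C.9.a.2 opens the Aim 2 analysis by stating that "the within-subjects analysis will compare drinking during phase 1 against phase 2 for three groups". It then describes two analyses:

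- **Interrupted time series.** "The phase indicator variable will measure change when entering phase 2", and a second week variable captures the change in slope. Table 1 lists only this model for the dutasteride responders: "Within-subject interrupted time series regression using mixed models. Dut-R: Is dut response maintained".
- **Restricted period.** It adds "a restricted period analysis focusing on the average of the last 4 weeks of phase 1" against the last 4 weeks of phase 2, because the early weeks of a phase may dilute the effect.

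For the dutasteride responders it then says that "the non-inferior margin will be 20% above the drinking levels during phase 1". No window is given, and neither analysis is named as carrying the test.

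Section 2.C.9.b, for 40 responders, 80% power and alpha 0.05, states that "the non-inferior margin limit would be an increase of 0.67 HDD/wk or 5 SDs/wk during the second 12 weeks dutasteride treatment". It gives no standard deviation of change, no responder mean and no sidedness, and it does not relate these figures to 20%.

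**The concern.** A non-inferiority conclusion is only as good as its margin and its reference level. Here the margin is a percentage in one section and an absolute amount in another, with nothing to convert one into the other. The reference is phase 1 drinking with no window.

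The window is the more serious gap. Responders are expected to drink much more early in phase 1 than in weeks 9-12, since the fall between the two is what makes them responders. A 12-week average therefore lies above the level that is supposed to be maintained, and the margin is then added on top of it. A group could give back much of its gain and still be declared non-inferior. Leaving the reference open also allows it to be chosen after the data are seen.

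**Working it through.** In what follows, drinks/wk means standard drinks per week, which the protocol abbreviates SD/wk.

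**Inputs**
- Margins: 20% (2.C.9.a.2); 5 drinks/wk and 0.67 heavy drinking days/wk (2.C.9.b).
- n = 40, 80% power, alpha 0.05 (2.C.9.b).
- Response: a cut of at least 60% in weeks 9-12 (2.C.1).
- Starting level: 48 drinks/wk, the group average in the earlier trial (2.B.2). It is used as an assumption, because the documents give no baseline for responders.

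**1. The plan's own figure.** For a paired test with no true change, margin = s × (z for 1−alpha + z for 80% power) / √n, where s is the standard deviation of the within-person change. Since s is not given, 5 drinks/wk cannot be reproduced. Solving backwards with √40 = 6.325:
- one-sided 0.05: s = 5 × 6.325 / (1.645 + 0.842) = 12.7
- one-sided 0.025: s = 5 × 6.325 / (1.960 + 0.842) = 11.3

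**2. Where the two margins agree.** 5 / 0.20 = 25 drinks/wk. For heavy drinking days, 0.67 / 0.20 = 3.35 per week. No responder level is given for heavy drinking days, so no conflict can be shown there.

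**3. Weeks 9-12 as reference.** A 60% cut from 48 leaves at most 0.4 × 48 = 19.2. Then 20% is at most 0.20 × 19.2 = 3.84 drinks/wk, and 5 drinks/wk is at least 5 / 19.2 = 26%. Agreement at 25 would need a baseline of at least 25 / 0.4 = 62.5.

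**4. All 12 weeks as reference.** Assume a straight-line fall from 48 to 19.2, then a flat course.
- Over 4 weeks: (40.8 + 33.6 + 26.4 + 9 × 19.2) / 12 = 273.6 / 12 = 22.8.
- Over 8 weeks: (44.4 + 40.8 + 37.2 + 33.6 + 30.0 + 26.4 + 22.8 + 5 × 19.2) / 12 = 331.2 / 12 = 27.6.

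| Fall complete | Phase 1 mean | 20% of mean | Limit (mean × 1.20) | Limit against 19.2 |
|---|---|---|---|---|
| at once | 19.2 | 3.84 | 23.04 | +20% |
| 4 weeks | 22.8 | 4.56 | 27.36 | +42.5% |
| 8 weeks | 27.6 | 5.52 | 33.12 | +72.5% |

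The absolute margin does not help on this reference: 22.8 + 5 = 27.8 (+45% on 19.2) and 27.6 + 5 = 32.6 (+70%). Even exactly no change from the 12-week mean would be a rise of 22.8 / 19.2 − 1 = 19% to 27.6 / 19.2 − 1 = 44% over weeks 9-12.

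**5. Power of the 20% test on weeks 9-12 (illustration only).** If s stays at the back-solved value:
- one-sided 0.05: 3.84 × 6.325 / 12.7 − 1.645 = 0.27, power about 60%
- one-sided 0.025: 3.84 × 6.325 / 11.3 − 1.960 = 0.19, power about 58%

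If s shrinks in proportion to the mean, power stays at 80%. The documents do not say which applies.

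**The case against.** The strongest defence is that the two sections do not conflict. Any percentage and any absolute margin meet at exactly one level. Here that level is 25 drinks/wk, inside the 22.8 to 27.6 range of step 4. Both 2.C.9.a.2 and 2.C.9.b use whole-phase wording, and 2.C.9.a.2 says so explicitly when it means the last 4 weeks. The figure in 2.C.9.b can also be read as the smallest margin that 40 responders support, not as a second definition. This stands to the extent that a reader who infers a proven arithmetic contradiction goes further than the documents allow.

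The same defence exposes the main weakness, however. The reading that makes the figures agree is the one that includes the weeks before response. And if 5 drinks/wk is only a detectable margin, the power of the 20% test is stated nowhere.

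It could also be said that the non-inferiority sentence directly follows the restricted-period text and so belongs to it. Its position does not settle this. That analysis is introduced as an addition, Table 1 names only the interrupted time series, and 2.C.9.b speaks of the second 12 weeks.

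Two further inferences are tempting but unsupported:
- **That the test is underpowered.** This depends on a back-solved standard deviation held fixed across reference levels.
- **That a truly maintained response would fail in the interrupted time series**, because the step is measured against a falling trend carried forward. The plan sets the margin above phase 1 levels, not above a projected trend. With drinking held at 19.2, the step exceeded 20% in only one of five assumed phase 1 shapes, under one coding of the second week variable.

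**Conclusion.** The point holds as an unreconciled margin and an unsuitable reference. Three parts need no assumption: the two margin statements, their agreement only at 25 drinks/wk, and the absence of any link between the test and a named analysis or window.

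The size rests on assumptions: a 48 drinks/wk start, a cut of exactly 60%, and a straight-line fall over 4 to 8 weeks. On these, the whole-phase 20% limit lies 43% to 73% above the weeks 9-12 level. An immediate fall would remove the excess and a slower one enlarges it. On weeks 9-12 at the same start, 5 drinks/wk is at least 26%, against the stated 20%.

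The consequence is confined to the claim that response is maintained, a single-arm comparison in about 40 selected responders. The randomised Aim 1 comparison is not affected. It should be fixed before the data are analysed.

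**What to change.** **Section 2.C.9.a.2.** Apply the Aim 2a non-inferiority test to the restricted-period comparison already planned: weeks 9-12 against the last 4 weeks of phase 2. State one margin on one scale (for example, a rate ratio below 1.20) and the one-sided alpha. Keep the interrupted time series and the whole-phase comparison as supporting analyses.

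**Section 2.C.9.b.** Use the same margin. Give the standard deviation of change and its source, and restate the power, or the margin that 40 responders can support, for that test. If 5 drinks/wk and 0.67 heavy drinking days/wk are the intended margins, put them in 2.C.9.a.2 and say what percentage of the expected weeks 9-12 level they represent.

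**Cost.** Only wording changes, since the needed weeks are already collected. There are two drawbacks. The stated power may fall. And because responders are selected on low drinking in weeks 9-12, some later rise is expected from selection alone, so the test is conservative. As an illustration with the back-solved standard deviation, a true rise from 19.2 to 21 drinks/wk would pass only about 21% to 26% of the time (32% to 37% if the standard deviation shrinks with the mean). The plan should acknowledge this when it justifies the margin.
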